## 5.8. Computed Tomography (CT) Scan

CT scans will be performed for research purposes to evaluate calcinosis burden/extent of calcinosis disease. One CT scan will be done for research purposes and patients may have up to two clinical CT scans during the protocol. The specific unique advantage of a CT scan and what it offers that other imaging modalities cannot accomplish is discussed in Section 10.1.2.5.

Participants will undergo non-contrast CT imaging of the trunk (thorax, abdomen, and pelvis) and extremities as a sensitive method to examine the morphology of the calcinosis (superficial plaques, deeper tumoral deposits, or fascial planar deposits), as

**Abbreviated Title:** Sodium Thiosulfate (STIC)

**Version Date:** July 07, 2023

well as the distribution of the lesions and their mass. 3D images will be reconstructed to obtain the volume of the lesions, which will be assessed over the course of the protocol.

After the CT data, have been acquired and stored, research software may be used to reconstruct images from the acquired data. This reconstruction could be performed on the scanner itself or off-line on a separate computer system. Data and images may be stored for future evaluation and additional processing.

The week 10 research CT scan is performed to analyze for response to therapy. This is the end of the treatment phase and when we expect to see the maximal effect of the study medication. Due to the extent and depth of disease often seen in this patient population, it is impossible to properly assess the amount of calcinosis by clinical exam. This CT scan will serve to quantify the change in the amount of calcinosis. Based on our prior experience, patients have had responses of a change in calcinosis as quickly as a few weeks, with some requiring longer therapy to show improvement. This time point we feel strikes a balance between giving patients enough time to have a response and not overly burdening them with additional time at or near the clinical center for additional infusions of study medication. We have performed CT scans of calcinosis in DM and JDM and have reviewed CT scans of other calcific disorders that have accurately reflected the areas of calcification, showing not only what has been determined from a thorough physical exam, but in addition, reveals additional areas of calcinosis that are not identifiable by examination. We feel that the quantitative assessment of calcinosis burden by CT imaging is critical in determining whether any improvement noted by patients or physicians is due to actual changes in calcinosis burden. CT scan changes have also correlated with clinical improvement in one published case (38).

Understanding whether the areas of calcinosis improve uniformly or not also is important information in designing future studies and for monitoring future patients on this therapy.

Study involvement can involve up to two clinical scans. The first CT scan would occur at week 0. If the patient had a CT scan in the year prior to this time they would not receive a CT scan at week 0 for clinical purposes as part of this protocol. This scan will serve to determine if the patient's symptoms are due to calcinosis and to ensure that they would not benefit more from surgery or local therapy than from treatment with the investigational drug in this protocol. The time point of week 0 is chosen since it is the closest time period when the patient is available to when study drug would be initiated. This will allow us to ensure patients would not better be managed with surgery at the time of deciding to implement medical therapy. This is important in determining that if a patient has specific acute problems due to their calcinosis whether or not it would be superior for them to receive surgical management or potentially other treatments compared to study medication. Also, if areas thought to have calcinosis from exam were found not to have calcinosis by CT imaging, then the patient could potentially fall into a less severe category and we would need to reassess the risk/benefit ratio of study participation for them.

The second potential clinical scan would occur at week 62. If the patient has signs of continued calcinosis severity by physical exam, symptoms, or DEXA scan, they will receive a CT scan to evaluate for re-accumulation of calcinosis. If the patient has had a clinically relevant CT scan in a time frame that makes the week 62 CT scan redundant, this CT scan will not be performed. This information will be used to decide if the patient should be tried on additional off-label therapy outside of the protocol. Change in calcinosis is decided in clinical practice primarily based on imaging studies, utilizing ionizing radiation, and physical exam. Patients with the severity of calcinosis we are

**Abbreviated Title:** Sodium Thiosulfate (STIC)

**Version Date:** July 07, 2023

enrolling are likely to still want additional therapy for their calcinosis if they did not have complete resolution as part of this study. Whether this therapy should be more sodium thiosulfate administered off label, surgery, another experimental agent, or another therapy would be guided by the clinical exam and imaging results. Important aspects of this decision will be whether the patient improved on sodium thiosulfate as part of the study and the severity of their current calcinosis. In discussing with other physicians this would entail imaging studies prior to initiating a new therapy for the same purpose of monitoring for improvement and knowing the patient's true calcinosis burden so the appropriate therapy can be chosen. We plan to do this clinical scan as part of this protocol so that it can be performed on the same scanner as prior scans to allow for more accurate comparison and assessment of the change in the lesions. The patient can also benefit from the decreased radiation offered by this scanner's research parameters versus a standard CT scan, and also, the data from the scan can be used for research purposes, in addition to its clinical purposes.

All efforts possible will be made to make the experience as tolerable as possible, which may include such activities as providing supportive padding, providing warm blankets during the test, supportive pads, cartoon animations of the CT gantry display for children to watch, and any other action that can increase the tolerability for that patient, with the understanding that all options may not be available for all patients.

## **5.9. Positron Emission Tomography - Magnetic Resonance Imaging (MRI/PET)**

MRI has proven useful for evaluating patients with myositis for disease activity.

Preliminary work from a pilot study we have performed shows that PET imaging can add additional information about areas of disease activity and particularly about calcinosis activity. We plan to further pursue these initial findings by performing MRI/PET in study participants. We will perform a MRI/PET from the base of the skull to the toes. All participants will receive a brief medical history to determine if they have any condition that would preclude a MRI/PET. These contraindications include, but are not limited to, pregnancy, implanted metal that is deemed to be dangerous, or age older than 95 years. A history of radiation exposure will be taken prior to enrollment and prior to performing any research study involving ionizing radiation. If the patient has received more than 0.5 rem for research purposes in the past 12 months prior to enrollment, we will delay enrollment until their time 0 would be 12 months or more from their last research radiation exposure. If the patient is already enrolled in the study and they have received more than 0.5 rem for research purposes outside of this protocol, we will review their situation with the DSMB and the IRB to decide whether to continue with currently planned research assessments involving radiation or to alter such assessments. All female subjects will receive a pregnancy test prior to this study and will be excluded from this testing if they are pregnant. All patients will have their blood sugar checked immediately prior to the study to ensure it is below 200 mg/dl, because hyperglycemia interferes with the uptake of radioactive glucose required for the PET scan. If blood glucose is found to be elevated, the medical team will work to safely lower the blood sugar and reassess if the blood sugar is at a level where the scan results would be interpretable. Prior to undergoing the scan, all subjects or their parents/guardians will complete a standard radiology questionnaire that determines other potential risks of the procedure that may have previously been missed. Prior to the scan patients will receive a detailed instruction sheet explaining that they need to minimize exercise for 48 hours prior to the scan,

**Abbreviated Title:** Sodium Thiosulfate (STIC)

**Version Date:** July 07, 2023

consume a high fat diet for 24 hours prior to the scan, and fast for 6 hours prior to the scan.

The MRI/PET will consist of having an IV line placed and receiving 10 mCi. of FDG. The patient will then sit in a quiet room for an uptake period of approximately one hour. The patient will then be placed on the scanner for the MRI/PET scan. These images will then be analyzed by a nuclear medicine physician and/or radiologist. If any abnormality the subject did not know about is detected by MRI/PET, the subject and the subject's physician will be informed so that further care can be provided. In pediatric patients, there is the potential to exceed the radiation safety limit of pediatric patients of 0.5 rem/year from each of these scans.

MRI/PET is scheduled to occur at week 0, 10, and 62 in adults and 0 and 62 in pediatric patients. If a patient has become pregnant, at week 62 they will receive a full body MRI instead of the MRI/PET. If a patient has no PET abnormalities on MRI/PET at week 0 they will not receive any further MRI/PET scans in the study.

All efforts possible will be made to make the experience as tolerable as possible, which may include such activities as providing supportive padding, providing blankets during the test, playing the patient music, providing videos or movies for the patient to watch during the study, and any other action that can increase the tolerability for that patient, with the understanding that all options may not be available for all patients.

For an in-depth review of the potential direct clinical benefits to the patient and the reasoning for what MRI/PET provides that the other imaging modalities being used do not, please refer to Section 10.1.2.6.

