### **3.4. Discussion on Timing of Imaging Time Points**

Wholebody MRI data collected as either a dedicated wholebody MRI or as part of a MRI/PET is collected at week -10, 0, 6, 10, 24, and 62. Time points -10 and 0 are needed to assess baseline muscle, pericalcinosis, and fascial edema at baseline. The baseline fluctuation in this disease is unknown and a baseline variance is needed as a comparator to the change over the treatment period to assess for drug benefit in these parameters which are all thought to be signs of active disease. Week 0 and 6 are needed to help in assessing if the patient is able to stop medication at the 6 week point. MRI is an important parameter for the physicians to assess for disease activity as well as to make sure all liquefied areas of calcinosis are visualized that may still benefit from treatment. This will also allow us to better understand the trajectory of response when used with the 0 and 10 week assessments. Week 10 is our primary end point assessment and will be used to assess if the study medication has improved either muscle or pericalcinosis inflammation/edema. As one of the main factors we are analyzing is the change in amount of calcinosis, it is also important to make sure we capture any liquefied areas of calcinosis that may be missed by CT scan. The week 24 and 62 week MRIs are for evaluation of long term effect. It is unknown how long the effect of this medication will last and these will allow us to determine if inflammation returns and the time line of a return in inflammation. This is important in thinking about developing re-dosing plans for future patients and for better elucidating the mechanism of action by determining if the changes in calcinosis burden and inflammation/edema are linked together or whether they appear to be independent.

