PET as part of a MRI/PET is performed at weeks 0, 10 in adults, and potentially week 62. PET imaging offers a way to look at metabolic activity of the calcinosis lesions. We have seen that calcinosis lesions can be PET active or not and can have different patterns of activity. Those lesions that have been PET active have tended to correspond to lesions the patients describe as new, active, or changing in some aspect. Based on some of the cases we have been part of it does not appear all calcinosis lesions respond equally to sodium thiosulfate and part of this may be due to their activity. Thus, we are obtaining PET imaging to assess for lesion activity to see if there is a correlation between PET activity and which lesions respond to therapy. To accomplish this, we need to know PET activity prior to study drug initiation (week 0). This will allow us to determine if specific types of calcinosis lesions based on PET activity respond better or worse to sodium thiosulfate. It will also allow us to see if the sodium thiosulfate affects the energy usage of calcinosis lesions in followup. The week 62 time point allows us to determine the metabolic changes from treatment. Also, if a differential effect is seen, it would allow a clinical opinion to be given of what lesions are most likely to respond in that patient to additional sodium thiosulfate, or even to generalize this knowledge to the treatment of other patients in the future. The 10-week evaluation in adults will allow us to evaluate the direct drug effect on lesion activity. A decrease in the energy consumption of lesions would help indicate that the medication is working through pathways besides purely causing chemical reabsorption which would not necessarily decrease energy consumption.

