b. Sodium thiosulfate treatments are administered 3 times/week, starting at Week 0 and continuing through Week 10

c. At Week -10, Week 0, Week 24, and Week 62, medication history and concomitant medications will be reviewed with the subject in detail; at all other visits, any changes occurring since the last evaluation will be assessed.

d. Photography will be performed more frequently than indicated if there's a noted change

e. If a DEXA scan has been performed within 6 months prior to initiation of the study, that will be used as the baseline DEXA evaluation

f. Iothalamate clearance not performed for children at Week -10 visit

g. Iothalamate clearance is optional at Week 24 and Week 62 if normal previously

h. Urine assessment will include calcium, phosphorus, pyrophosphate, creatinine, citrate, and urate; while receiving sodium thiosulfate infusions, evaluations for renal function and urinary excretion of calcium will be performed weekly. They will use a split collection with Cr, Na, CA, Mg, P, and urate coming from the non-acidified container. Cr, citrate, and oxalate will be collected from the acidified container.

i. While receiving sodium thiosulfate infusions, evaluations for renal function, metabolic acidosis, PT/PTT, and serum calcium will be performed weekly

**Abbreviated Title:** Sodium Thiosulfate (STIC)

**Version Date:** July 07, 2023

	Pre-treatment				Treatment										Follow-up	
	Week															
	Screening	-10	-4	0	1	2	3	4	5	6	7	8	9	10	24	62
j.	These are the times for formal review for adverse events. In addition, patients, will have contact information to reach the study team to contact them for any expected adverse events they experience at other times.															
k.	If needed, a PICC or Port-A-Cath line will be inserted to maintain IV access for multiple infusions and this may occur prior to a scheduled visit.															
l.	Only performed if the CT scan during that visit does not include the kidneys.															
m.	If a patient has become pregnant or is breastfeeding and is unable to receive a MRI/PET at this visit they will instead receive a whole body MRI.															
n.	At week 10 adults patients will receive a MRI/PET while pediatric patients will receive a whole body MRI instead.															
o.	May be performed by their home physician															
p.	If the MRI/PET is not performed at this point a whole body MRI if safe will be performed instead.															

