q.	If the MRI/PET machine is non-operational at this time point for the adult patients enrolled, the patients will instead have a CT/PET and a whole body MRI. Only three patients in the study may get CT/PET in place of MRI/PET.															

**Abbreviated Title:** Sodium Thiosulfate (STIC)

**Version Date:** July 07, 2023

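### Section 5.9 and Table 4 give adults with a negative Week 0 PET no Week 10 whole-body MRI, against Section 3.4, and Week 0–10 PET change is observable only in adults positive at Week 0, with no lead-in scan

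*Combined protocol and SAP*

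**What the plan says.** On MRI, Section 3.4 says that whole-body data, "as either a dedicated wholebody MRI or as part of a MRI/PET is collected at week -10, 0, 6, 10, 24, and 62", serve the study, and it treats Week 10 as the main time point for judging muscle and pericalcinosis edema. It makes no exception for PET-negative patients.

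On MRI/PET, Section 5.9 gives the schedule: "MRI/PET is scheduled to occur at week 0, 10, and 62 in adults and 0 and 62 in pediatric patients". It then adds the stopping rule: "If a patient has no PET abnormalities on MRI/PET at week 0 they will not receive any further MRI/PET scans in the study". It names no replacement scan for patients stopped this way.

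The notes to Table 4 (Appendix B) that bear on a missing MRI/PET are:

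- Note n, on the Week 10 MRI/PET: "At week 10 adults patients will receive a MRI/PET while pediatric patients will receive a whole body MRI instead".
- Note p, on the Week 62 mark of the whole-body MRI row: "If the MRI/PET is not performed at this point a whole body MRI if safe will be performed instead".
- Note q, on the MRI/PET marks: "If the MRI/PET machine is non-operational at this time point for the adult patients enrolled, the patients will instead have a CT/PET", together with a whole-body MRI.
- Note m, on the Week 62 MRI/PET, which covers pregnancy or breastfeeding.

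On the use of PET, Section 3.4 presents the adult Week 10 scan as showing what the drug itself does to lesion activity. It adds: "A decrease in the energy consumption of lesions would help indicate that the medication is working through pathways besides purely causing chemical reabsorption". PET is planned at Week 0, at Week 10 in adults, and possibly at Week 62. There is no PET at Week -10.

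**The concern.** There are two separate problems.

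The first is a conflict over the schedule. Section 2.1 compares secondary outcomes, imaging included, as change from Week -10 to 0 against change from Week 0 to 10. A patient without a Week 10 MRI cannot contribute to that paired comparison. The gap would not be random. Section 3.4 reports that PET-active lesions tended to be the ones patients called new, active or changing, so PET-negative adults are probably those with quieter disease. With 13 completers planned, each one lost matters to an MRI summary.

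The second is how the PET change is read. Patients are re-scanned only if their first scan was abnormal, so part of any later fall is expected from selection alone. For MRI, Section 3.4 argues that untreated variation must be known before a treatment-period change can be credited to the drug. For CT it concedes the missing Week -10 scan as a weakness. It makes no such concession for PET, although PET also lacks a Week -10 scan.

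**Working it through.** **Schedule for an adult with no PET abnormality at Week 0**

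| Week | Section 3.4 | Section 5.9 with Table 4 |
|---|---|---|
| -10 | MRI | MRI |
| 0 | MRI | MRI, within MRI/PET |
| 6 | MRI | MRI |
| 10 | MRI | none |
| 24 | MRI | MRI |
| 62 | MRI | MRI, by note p |

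The sources differ only at Week 10. Taking the notes in turn at that visit: n gives the substitute to children; p is attached to Week 62; q requires a machine that is not working; m concerns pregnancy or breastfeeding at Week 62. None is triggered by a negative PET in an adult.

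Table 4 should be checked against the typeset page. In the text copy the first header has lost Week 10, and the CT rows carry a Week 24 mark where Sections 3.4 and 5.8 place the research CT at Week 10. The reading above does not depend on column positions alone. The MRI/PET weeks are stated in words in Section 5.9, the notes are legible, and the whole-body MRI and MRI/PET rows together give exactly the six weeks listed in Section 3.4.

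**Number at risk**

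This cannot be derived. The documents give no PET-negative proportion. The number of adults is not fixed either: the planned balance is between juvenile and adult DM, and the screening form defines juvenile disease by age at diagnosis, so an adult participant may have JDM.

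**PET change with no drug effect (illustration, all inputs assumed)**

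Let the patient-level PET score be standard normal at both visits with test-retest correlation r. A fraction q falls below the threshold at Week 0 and is not re-scanned. Then

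E(change | re-scanned) = −(1 − r) × φ(z_q) / (1 − q),

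where z_q is the q-quantile and φ the standard normal density. The selection factor φ(z_q)/(1 − q) is:

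- q = 10%: 0.1755 / 0.90 = 0.195
- q = 25%: 0.3178 / 0.75 = 0.424
- q = 50%: 0.3989 / 0.50 = 0.798

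Multiplying by −(1 − r) gives the expected change in SD units:

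| r | q = 10% | q = 25% | q = 50% |
|---|---|---|---|
| 0.9 | −0.02 | −0.04 | −0.08 |
| 0.7 | −0.06 | −0.13 | −0.24 |
| 0.5 | −0.10 | −0.21 | −0.40 |

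Simulation with the same inputs agrees, and the mean change over all patients is 0. In those runs 33% to 48% of re-scanned patients still rise. Of those negative at Week 0, 14% to 68% would have crossed the threshold at the second scan, and none of these would be observed.

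The plan states no figure of its own on this point, so there is nothing to reproduce.

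**The case against.** The strongest reply on MRI is that Section 3.4 already settles it. It allows a dedicated scan at Week 10, and Section 5.9 stops MRI/PET, not MRI. Read together, a dedicated MRI fills the gap. This stands in part. A reader might infer that PET-negative adults certainly lose the Week 10 MRI; the documents do not support that, because Section 3.4 commits to the scan. What they show is an unresolved conflict. The visit table, which staff are likely to work from, omits the scan, while notes n and p show that substitution was thought through for children and for Week 62.

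On PET, a reader might infer that the effect is measured only where activity can fall. That is not so. Section 5.9 images from skull base to toes, so lesions inactive at Week 0 are seen again in re-scanned patients, and Section 10.1.2.6 treats later increases as informative. The blind spot is narrower: new activity in patients who were negative at Week 0.

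The size of the PET effect is also open to challenge. Patients are selected for extensive, moderate to severe calcinosis and may have well over 100 lesions, so few may have a wholly negative scan. At 10% negative and r = 0.9 the shift is negligible.

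Limiting PET has a sound reason, since each adult MRI/PET adds 0.67 rem. Nothing here calls for more PET. Finally, the mechanism statement is hedged, PET carries no confirmatory test of its own, these adults keep their other MRI visits, and Section 8.1 says mixed models will be considered for quantitative secondary outcomes over time. These points limit the consequence. They do not remove the conflict or supply a comparator for PET.

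**Conclusion.** The point holds as a contradiction to be reconciled and an interpretation to be narrowed. Section 5.9 and Table 4 provide no Week 10 whole-body MRI for PET-negative adults, whereas Section 3.4 promises one to everybody. Following the former would remove the Week 0–10 MRI change selectively in that group, to an extent the documents do not allow us to count.

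A Week 0–10 PET fall, observed only in adults abnormal at Week 0 and without an untreated interval for comparison, cannot be credited to the drug by itself. The direction of the selection effect follows whenever r is below 1 and some patients are screened out. Its size, −0.02 to −0.40 SD in the illustration, rests entirely on the assumed q and r and on normality.

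No one should read this as a threat to the primary analysis. The primary outcome is the calcinosis activity VAS, which does not depend on the MRI/PET schedule. Only secondary and mechanistic imaging results are affected.

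**What to change.** 1. Reconcile Section 5.9 and Table 4 with Section 3.4: apply note p (whole-body MRI, if safe, when the MRI/PET is not performed) at Week 10 as well as Week 62, and say so next to the stopping rule in Section 5.9.
2. In Section 3.4, describe the Week 0–10 PET change as descriptive, lacking a lead-in comparator, and conditional on an abnormal Week 0 scan.
3. Report how many adults were not re-scanned because of a negative Week 0 PET.
4. Analyse all lesions in re-scanned patients, including those not avid at Week 0, so that increases count alongside decreases.

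The cost is one table note and a few sentences. The MRI is already promised in Section 3.4, uses no gadolinium (Section 5.7) and adds no radiation; no extra PET is needed. The downside is a weaker PET claim about mechanism.
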